Hysterosalpingo-lidocaine-foam sonography procedure:

- 1. HyLiFoSy-PD procedure will be performed in proliferative phase of the cycle (Days 5 12).
- Clinical evaluation including history taking and a baseline twodimensional (2D) TV-US examination will be carried out prior to starting the HyLiFoSy-PD procedure.
- 4. Administration of a non-Steroidal anti-inflammatory drug (NSAID) rectal suppository will be carried out one hour before the procedure (diclofenac sodium 100 mg), in addition to antibiotic prophylaxis using

oral azithromycin for 3 days, starting the day before the procedure and continued for one day afterwards

- 5. In the dorsal lithotomy position, the cervix will be visualized with a Cusco speculum, cleaned with an antiseptic, then a 5- or 6- Fr pediatric Foley's balloon catheter will be introduced into the cervical canal with the help of a Bozeman forceps and a tenaculum if necessary.
- 6. The balloon will be positioned in the lower uterine cavity and inflated with 2 ml of saline to prevent backflow of contrast medium through the cervix, then the speculum will be removed. The TV-US probe will be reintroduced in a longitudinal plane to confirm correct placement of the catheter.
- 7. The foam contrast agent will be created by mixing 3–4mL of 2% lidocaine gel (Xylocaine Jelly 2%, Atrazeneca, Sweden) with 16–17mL of saline. The assistant will create the foam immediately before application by shaking the mixture (approximately 10–20 times) between two connected syringes. This will be done until a whitish suspension is obtained.
- 8. Repeated small doses (3-5 ml) of the lidocaine-made foam will be infused slowly into the uterine cavity while observing the flow of the contrast medium in each fallopian tube.
- 9. Using greyscale US, flow over the whole length of the tube, fimbrial outflow, or peritoneal spillage of contrast will provide definite evidence

KASR ALAINY

of tubal patency. Contrast filling of the uterine cavity without cornual flow will suggest tubal occlusion.

- 10.PD will then be added to re-assess tubal patency and assess the "flaming tube" sign. Flaming sign interpretation will be classified as: strong, weak, or absent.
- 11.Images will be stored as 2D and PD still images and video clips.HyLiFoSy-PD will be performed by experienced sonographers at our unit, who will be blinded to the results of LDT.

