- 12.Patients will be asked about the degree of discomfort or pain they felt during and immediately after the procedure. Using categorical verbal rating scale (VRS),(28) Procedure will be stopped if a patient experiences severe pain.
- 13.Patients will be followed up overnight and monitored for any other procedure-related side effects or complications.
- 14. Within a week following the HyLiFoSy-PD procedure, standard LDT will be carried out by experienced endoscopists who will be blinded to the results of HyLiFoSy-PD. During LDT, tubal patency will be tested using methylene blue dye. Tubal evaluation during LDT will be classified as: patent with immediate spill, patent with delayed spill, or blocked.

Possible Risk (mention if there is any risk or not)

Side effects such as vasovagal reactions, allergic reaction, and venous intravasation have been reported in literature in hysterosalpingo-foam studies. However, in our previous hysterosalpingo-lidocaine-foam sonography study, none of these side effects were encountered. For the possible risk of infection, all patients will be given prophylactic antibiotics. In addition, any case with visible hydrosalpinx or signs or symptoms of PID on US prior to performing HyLiFoSy-PD will not perform the procedure.

9. Study outcomes:

Primary outcomes

1. Diagnostic accuracy of HyLiFoSy and HSG with reference to LDT, in terms of sensitivity, specificity, positive predictive value, negative predictive value, and overall accuracy.

Secondary outcome parameters

1 -Diagnostic accuracy of adding power doppler to the HyLiFoSy.

2-Evaluate the procedure associated pain

3-Evaluate the procedure duration

4-Percentage of failed or inconclusive attempts and possible reasons for

that

5-Incidence and rate of potential complications for example: vasovagal and allergic reactions, venous intravasation.

10. Sample size: Using the following equation:(29)

$$N_{\text{Disease}} = \frac{\left\{z_{1-\alpha/2}\Lambda + z_{1-\beta}\sqrt{\Lambda^2 - \zeta^2(3+\Lambda)/4}\right\}^2}{\Lambda\zeta^2}$$

where $\Lambda = (1 - Se_1)Se_2 + (1 - Se_2)Se_1$ and $\zeta = (1 - Se_1)Se_2 - (1 - Se_2)Se_1$.

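### Secondary outcome 1 (adding power Doppler) has no locked greyscale call and no rule turning the three-grade flaming-tube sign into patent or blocked

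*Combined protocol and SAP*

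**What the plan says.** All references are to the combined protocol and SAP.

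- **Section 9, secondary outcome 1:** "Diagnostic accuracy of adding power doppler to the HyLiFoSy".
- **Section 8, procedure step 9 (greyscale, patent):** "Using greyscale US, flow over the whole length of the tube, fimbrial outflow, or peritoneal spillage of contrast will provide definite evidence" of patency.
- **Step 9 (greyscale, occluded):** "Contrast filling of the uterine cavity without cornual flow will suggest tubal occlusion".
- **Step 10 (Doppler):** "PD will then be added to re-assess tubal patency and assess the 'flaming tube' sign. Flaming sign interpretation will be classified as: strong, weak, or" absent.
- **Step 11:** 2D and Doppler stills and clips are kept. The sonographers are blinded to LDT; no other blinding of the scan is described.
- **Step 14 (reference standard):** "Tubal evaluation during LDT will be classified as: patent with immediate spill, patent with delayed spill, or blocked".
- **Section 11:** accuracy is to be reported as sensitivity, specificity, predictive values and overall accuracy. The only comparison named is one-way ANOVA.

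**The concern.** The value of adding a test is the difference between two accuracies measured on the same tubes: greyscale alone, and greyscale plus Doppler. Each needs its own patent-or-blocked call, made by a stated rule. Two things are missing.

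First, nothing makes the greyscale call final before Doppler is switched on. If it is written down only at the end of the scan, it can move towards what Doppler showed. The two results then agree more than they should and a real gain shrinks towards zero. The figure reported as greyscale accuracy would also contain Doppler information.

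Second, the Doppler sign has three grades but sensitivity and specificity need two. The plan does not place the weak grade on either side, and does not say how a tube is called when Doppler and greyscale disagree. If those rules are set once LDT results are known, the more favourable version can be picked, and the reported accuracy is optimistic.

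The two effects pull in opposite directions, so the net bias cannot be predicted or corrected afterwards.

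**Working it through.** **1. How each test becomes a patent or blocked call**

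| Test | Patent | Blocked | Gap |
|---|---|---|---|
| HSG (section 8, interpretation of results) | Dye along the whole tube, with immediate or delayed spill | No passage at the cornu, or only part of the tube filled | None of note |
| Greyscale (step 9) | Whole-length flow, fimbrial outflow or spill | Cavity fills with no cornual flow | Cornual flow that goes no further is unclassified |
| Doppler (step 10) | Not stated | Not stated | No cut-off for three grades; no rule for disagreement with greyscale |
| LDT (step 14) | Two of the three categories are labelled patent | The third | None |

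Doppler is the only test with no dichotomy at all.

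**2. What the missing cut-off can do**

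Compare the rule absent = blocked with the rule absent or weak = blocked. Moving from the first to the second

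- raises sensitivity by P(weak | blocked on LDT), and
- lowers specificity by P(weak | patent on LDT).

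The documents give neither probability, so the size of the shift cannot be computed from them. Any percentage put forward would only restate an assumption about how common the weak grade is.

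**3. Scale from the plan's own planning figures**

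Section 10 gives sensitivities of 0.55 (HSG) and 0.90 (HyLiFoSy-PD), power 90%, a 95% confidence level and prevalence 30%. Putting these into its formula:

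- Λ = 0.45 × 0.90 + 0.10 × 0.55 = 0.46
- ζ = 0.405 − 0.055 = 0.35
- N(diseased) = {1.96 × 0.46 + 1.2816 × √(0.46² − 0.35² × 3.46/4)}² / (0.46 × 0.35²) = 30.83
- 30.83 / 0.30 = 102.8, against the stated 100. Thirty diseased women give exactly 100.

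The sample size reproduces closely and is not in dispute here. It supplies the denominators: about 30 diseased and 70 non-diseased women among 100, if the analysis is per woman (an assumption, since the unit of analysis is not stated).

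- One diseased woman whose call hinges on the weak grade: 1/30 = 3.3 points of sensitivity.
- One non-diseased woman: 1/70 = 1.4 points of specificity.

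**4. How few calls decide the comparison**

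Assume Doppler changes calls in one direction only among 30 diseased women, tested by exact two-sided McNemar (p = 2 × 0.5^k for k changed calls).

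- k = 5: p = 0.0625
- k = 6: p = 0.031

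One tube graded weak and coded one way or the other can therefore move the result across 0.05. The chance of reaching six changes is 7%, 29%, 57% and 80% for true change rates of 10%, 15%, 20% and 25%.

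**5. Which call is the primary index test?**

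Primary outcome 1 (section 9) names HyLiFoSy. The aim at the end of section 4 and the 90% sensitivity in section 10 name HyLiFoSy-PD, while the section 5 objective leaves Doppler out. If the primary result is the Doppler-inclusive call, the missing rules reach the main comparison with HSG as well.

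**The case against.** Several points on the other side are sound.

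- **Order.** A reader might infer that doing Doppler after greyscale is itself a flaw. It is not: the outcome is about adding Doppler, and greyscale first is the natural order for that question.
- **Operator.** A reader might infer that one person makes both calls. Step 11 speaks only of experienced sonographers and does not say who makes which call.
- **Extra foam.** Step 8 says "Repeated small doses (3-5 ml) of the lidocaine-made foam will be infused slowly into the uterine cavity", and it is tempting to conclude that Doppler follows more foam and gets the credit for late filling. Step 10 mentions no further dose, so this is possible but not documented.
- **Objective.** It would be too strong to say that the study's objective cannot be met. Section 5 concerns HyLiFoSy against HSG; adding Doppler is a secondary outcome.
- **Post hoc choice.** Silence is not a plan to choose the cut-off after LDT. The documents leave that open; they do not announce it. Blinding the sonographers to LDT protects the grading, but not the later coding of grades into two classes.
- **Two outputs.** Step 10 can be read as yielding a patency call plus a purely descriptive grade. No cut-off is then needed, but the criteria for the Doppler patency call are stated nowhere, so the gap moves rather than closes.
- **Stored images.** The 2D clips could be read later without Doppler. That is a partial safeguard: no such read is planned, it would not fully replace the real-time call, and it cannot supply a missing rule.

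**Conclusion.** The point stands in limited form. As written, secondary outcome 1 has no defined 2x2 table for greyscale plus Doppler, and the greyscale-only result is not protected from revision once Doppler has been seen. The first gap allows optimistic accuracy if the rule is set after LDT; the second can hide a gain.

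The size of either effect cannot be derived from the documents. The 3.3-point step per diseased woman rests on a per-woman analysis with about 30 diseased women, and the six-call threshold also assumes one-directional changes. Both show how sensitive the result is to a few calls; neither estimates the bias.

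The primary outcome is affected only if its HyLiFoSy result is the Doppler-inclusive call, which the plan needs to settle. The remedy is a cheap improvement, best made before recruitment because a real-time greyscale call that was not recorded cannot be fully recovered.

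**What to change.** 1. **Steps 9-10.** Enter the greyscale call for the right and the left tube on the case form before Doppler is switched on, with no later change, and use it as the greyscale-only result. Include a category for tubes that meet neither step 9 criterion.
2. **Before the first LDT.** State which grades count as patent, for example strong or weak = patent and absent = blocked, with the other cut-off as a sensitivity analysis. State also how a tube with discordant greyscale and Doppler results is called.
3. **Sections 9 and 11.** Compare the two calls with a paired analysis that allows for two tubes per woman, such as a McNemar-type comparison with clustering by woman. State whether the HyLiFoSy result in primary outcome 1 is the greyscale call or the Doppler-inclusive call, and use one name for it throughout.

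Cost: a few seconds per scan, a few more entries on the case form and a little more analysis work. No extra procedure, reader or patient is needed.

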Women in the reproductive age group between 18- and 40-years old presenting with primary or secondary infertility who underwent HSG in the previous 5 years as a part of their infertility work-up with availability of good-quality HSG images, & did not get pregnant in this period, and gave no history of incidences that might affect their tubes, such as : abdominal surgery or laparoscopy, pelvic inflammatory disease, smoking, and intrauterine device insertion.

Women fitting these inclusion criteria and scheduled for LDT as part of their infertility work up will be considered. HyLiFoSy-PD will be carried out few days before the already scheduled LDT.

The study will be conducted in the Cairo fetal medicine unit, department of Obstetrics and gynecology, Cairo university.

Inclusion criteria:

- 1. Age group (18-40)
- 2. Informed signed Written consent.
- 3. Scheduled for LDT as a part of their infertility management

- 4. Have undergone HSG in the previous 5 years with the availability of good-quality HSG images.
- 5. No incident factors that might have affected the tubal status after she underwent HSG within the previous 5 years, such as ; abdominal surgery or laparoscopy, pelvic inflammatory disease, smoking, and intrauterine device insertion.

Exclusion criteria:

Women with any of these factors will be excluded:

- 1. LDT scheduled for a therapeutic purpose due to a known tubal or ovarian pathology
- 2. Lack of good-quality HSG images.
- 3. Withdrawal of consent.
- 4. Using contraception
- 5. Women outside reproductive age
- 6. Known allergy to lidocaine
- 7. Active pelvic inflammatory disease
- 8. Undiagnosed genital tract bleeding.
- 9. Evident tubal pathology (such as hydrosalpinx) or pregnancy diagnosed by transvaginal ultrasound (TV-US) prior to performing HyLiFoSy-PD

Methodology in details

Interpretation of HSG results:

Review of the HSG films will be done for assessment of the tubal patency; tubes will be considered patent if the dye is seen throughout their whole length and till their ends with a positive immediate spill or a spill in the delayed film. If the dye does not pass through one or both cornual ends, or if a part of the tube is seen filled with dye but not the whole length then tubal obstruction will be considered. Patients with hydrosalpinx seen by HSG are to be assessed first by US if no visible hydrosalpinx is seen by US and she has no signs of PID then she can proceed to the HyLiFoSy-PD procedure.

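### Neither the sonographers nor the endoscopists are masked to HSG, although every woman has one at entry and HSG is one of the two tests in the primary comparison

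*Combined protocol and SAP*

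**What the plan says.** All references are to the combined protocol and SAP.

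- **Masking of the sonographer** (section 8, HyLiFoSy procedure, step 11): the scan is "performed by experienced sonographers at our unit, who will be blinded to the results of LDT".
- **Masking of the endoscopist** (same list, step 14): "standard LDT will be carried out by experienced endoscopists who will be blinded to the results of HyLiFoSy-PD".
- **Order of tests** (section 8, population): "HyLiFoSy-PD will be carried out few days before the already scheduled LDT". Step 14 puts LDT within a week of the scan.
- **HSG at entry** (section 8, population and inclusion criterion 4): the study takes women "who underwent HSG in the previous 5 years as a part of their infertility work-up", and criterion 4 reads "Have undergone HSG in the previous 5 years with the availability of good-quality HSG images".
- **Steps before the scan** (procedure, unnumbered item after step 1): "Clinical evaluation including history taking and a baseline twodimensional (2D) TV-US examination will be carried out prior to starting the HyLiFoSy-PD procedure".
- **Use of HSG before the scan** (section 8, Interpretation of HSG results): "Review of the HSG films will be done for assessment of the tubal patency", and "Patients with hydrosalpinx seen by HSG are to be assessed first by US".
- **What is compared** (section 5 and section 9, primary outcome): the difference in accuracy between HyLiFoSy and HSG, each judged against LDT.

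Nothing else in the text withholds HSG films or results from the sonographer or the endoscopist.

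**The concern.** Three tests are done in a fixed order: HSG, then HyLiFoSy-PD, then LDT. The two masking rules protect the HyLiFoSy-PD and LDT pair. They leave HSG, the earliest result, open to both later readers.

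This matters because HSG is one of the two index tests and not just background information. A sonographer who knows the HSG may move a HyLiFoSy-PD call towards it or away from it, so the two index results are no longer obtained independently. An endoscopist who knows it may move the LDT call, which is the reference that scores both tests. Either would act on the primary comparison.

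The plan contains two possible routes for disclosure to the sonographer: the history taken before the scan, in women whose HSG belongs to the same infertility work-up, and the ultrasound check prompted by hydrosalpinx on HSG. The plan does not say who performs either step, so these are possible routes and not shown ones.

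**Working it through.** **Step 1. Who is masked to what.**

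| Reader | HSG | HyLiFoSy-PD | LDT |
|---|---|---|---|
| Sonographer (step 11) | not stated | own test | masked; LDT not yet done at the live scan |
| Endoscopist (step 14) | not stated | masked | own test |

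Both empty cells concern HSG. For live reading, the order of tests already achieves the sonographer's one masking rule.

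**Step 2. The plan's own figure.** Section 10 uses sensitivities 0.55 (HSG) and 0.90 (HyLiFoSy-PD), 90% power, 95% confidence and prevalence 30%. With its formula:

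- Λ = 0.45 × 0.90 + 0.10 × 0.55 = 0.46
- ζ = 0.45 × 0.90 − 0.10 × 0.55 = 0.35
- N with disease = 30.83, and 30.83 / 0.30 = 102.8, so 103 against the stated 100

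The stated size reproduces closely and does not depend on masking.

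**Step 3. How far one changed call moves the result.** This is not an estimate of bias. Inputs: 30 blocked women (30% of 100), one call per woman, tests independent given tubal status.

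- Expected true positives: HSG 30 × 0.55 = 16.5; HyLiFoSy 30 × 0.90 = 27.
- Baseline difference: (27 − 16.5)/30 = 0.350.
- Discordant blocked women: 30 × 0.45 × 0.90 = 12.15 (HyLiFoSy positive, HSG negative) and 30 × 0.10 × 0.55 = 1.65 (the reverse), total 13.8.

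One call changed to match HSG:

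| Changed call | Calculation | Difference | Shift |
|---|---|---|---|
| HyLiFoSy to negative, blocked woman, HSG negative | (26 − 16.5)/30 | 0.317 | −0.033 |
| HyLiFoSy to positive, blocked woman, HSG positive | (28 − 16.5)/30 | 0.383 | +0.033 |
| LDT to patent, blocked woman, HSG negative, HyLiFoSy positive | (26 − 16.5)/29 | 0.328 | −0.022 |
| LDT to patent, blocked woman, HSG negative, HyLiFoSy negative | (27 − 16.5)/29 | 0.362 | +0.012 |
| LDT to blocked, patent woman, HSG positive, HyLiFoSy negative | (27 − 17.5)/31 | 0.306 | −0.044 |
| LDT to blocked, patent woman, HSG positive, HyLiFoSy positive | (28 − 17.5)/31 | 0.339 | −0.011 |

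The shifts run from about 0.01 to 0.04 and take both signs. The last two rows are not remote: with the HSG specificity of 87% in section 4, about 70 × 0.13 = 9.1 patent women would have a positive HSG, against 30 × 0.45 = 13.5 blocked women with a negative one.

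A call can also move away from the HSG. For example, LDT called patent in a blocked woman with HSG positive and HyLiFoSy negative gives (27 − 15.5)/29 = 0.397, a shift of +0.047. The table therefore does not settle the direction, and the documents give nothing from which to derive how many calls would change.

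**The case against.** **The documents do not show that readers will see the HSG.** This stands. A reader might infer that the calls will be influenced, or that the comparison is biased in favour of one test. The text supports neither. It does not say who takes the history or who makes the hydrosalpinx check. Every woman has a baseline transvaginal scan anyway, so that check need not reveal the HSG to the sonographer. It also applies only to women with hydrosalpinx on HSG, and those with hydrosalpinx visible on ultrasound are excluded. What remains is that nothing in the plan prevents disclosure.

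**The arithmetic says nothing about masking.** This stands too. One changed call among about 30 moves a proportion by about 1/30 whatever the cause. It shows sensitivity to single calls, and only for sensitivity, although section 9 also lists specificity, predictive values and overall accuracy.

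**Patency criteria are set in advance and images are stored.** This stands in part. Set criteria limit the influence of expectation but do not remove it. A masked re-read of stored clips could partly check the HyLiFoSy-PD calls. The plan mentions no stored LDT recording, so the reference calls could not be checked in that way.

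**The endoscopist may need the HSG.** LDT is a clinically scheduled operation, and full masking may not be workable. This stands and limits what can be asked in step 14.

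**A step may be missing from the text read.** The numbering of the procedure list passes from 1, through an unnumbered item, to 4. Nothing suggests that a lost item concerned masking, but the original should be checked.

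**Conclusion.** The point holds as a gap in masking. The plan masks the sonographer to a result that does not yet exist at the live scan, masks the endoscopist to one of the two index tests, and masks neither to HSG. Followed as written, it lets one index test inform the other, and lets it inform the reference.

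It does not show that bias will occur. Its direction and size cannot be determined from the documents; the shift of about 0.01 to 0.04 per call changed to match HSG is for scale only. That range rests on the plan's own sensitivities and prevalence, one call per woman, and independence of the tests given tubal status.

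A reader might also infer that the HyLiFoSy-PD and LDT pair is unprotected, or that the sample size is affected. Neither follows: that pair is protected in live reading, and section 10 does not depend on masking.

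This is more than a missing detail, because fixing the order of recording changes how the study is run and protects the primary comparison at little cost. It is a cheap improvement.

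**What to change.** 1. **Step 11.** Add that the sonographer records the HyLiFoSy-PD result for each tube, greyscale first and then power Doppler, before seeing the HSG films or patency result. Leave the history taking and the hydrosalpinx check in place, and note on the form any HSG information disclosed through either.
2. **Step 14.** Keep the masking to HyLiFoSy-PD. Add that LDT patency for each tube is recorded without reference to the HSG where the surgeon does not need it, and otherwise note that the HSG was known.
3. **Interpretation of HSG results.** State that the film review described there is the HSG reading analysed, and that it is recorded before HyLiFoSy-PD and LDT. The section reads most naturally that way but does not say so.

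**Cost.** Protocol wording, a set order of recording and one added item on each of two forms. No added procedure and no added patients. The downside is logistical: the person who reviews the films and screens for hydrosalpinx should not be the sonographer. Five investigators are listed, but their roles in reading, scanning and operating are not given, so it is an assumption that the team can separate these tasks. An endoscopist may sometimes need the HSG, so masking of LDT may stay incomplete; the note on the form makes that visible.

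### The only stated complication follow-up is overnight, so the reported complication rate may miss a pelvic infection that becomes apparent between the first night and laparoscopy

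*Combined protocol and SAP*

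**What the plan says.** All of the relevant text is in the combined protocol and SAP.

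- **Complication follow-up (section 8, HyLiFoSy-PD procedure, step 13):** "Patients will be followed up overnight and monitored for any other procedure-related side effects or complications". No other complication follow-up is described.
- **Infection as a risk (section 8, Possible Risk):** "For the possible risk of infection, all patients will be given prophylactic antibiotics". The other measure is a screen before the test: "any case with visible hydrosalpinx or signs or symptoms of PID on US prior to performing HyLiFoSy-PD will not perform the procedure".
- **Antibiotic course (section 8, step 4):** "oral azithromycin for 3 days, starting the day before the procedure and continued for one day afterwards".
- **Outcome (section 9, secondary outcome 5):** "Incidence and rate of potential complications for example: vasovagal and allergic reactions, venous intravasation". The list is open, infection is not among its examples, and no time window is attached.
- **Next contact (section 8, step 14):** "Within a week following the HyLiFoSy-PD procedure, standard LDT will be carried out by experienced endoscopists". What this step asks to be recorded is tubal patency. It mentions no check for complications of the earlier test.

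**The concern.** The plan names a risk, promises a complication rate, and already has a second contact scheduled with every woman, but it does not connect the three. Prophylaxis and the pre-procedure screen are meant to prevent infection. Neither measures whether infection occurred afterwards. Read together, steps 4 and 13 mean that stated observation stops at about the time the antibiotic course ends, so no stated observation falls after prophylaxis.

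The plan's own eligibility rules suggest that the interval deserves a record. Inclusion criterion 5 treats pelvic inflammatory disease after the HSG as an event that could have altered the tubes. There is no matching record for the interval between HyLiFoSy-PD and LDT.

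At stake is how a low or zero complication count can be read. If a report states that no complications occurred, a reader will probably take that to include infection. Under the stated window, the count would describe only what was visible by the next morning.

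**Working it through.** **1. The denominator.** The complication rate would be computed on the recruited women, so the plan's sample size comes first. Section 10 uses a paired-sensitivity formula with sensitivities 0.55 and 0.90, 95% confidence (taken as two-sided), 90% power and 30% prevalence.

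- Λ = 0.45 × 0.90 + 0.10 × 0.55 = 0.46
- ζ = 0.45 × 0.90 − 0.10 × 0.55 = 0.35
- N with disease = {1.960 × 0.46 + 1.282 × √(0.46² − 0.35² × 3.46/4)}² / (0.46 × 0.35²) = 30.83
- 30.83 / 0.30 = 102.8, close to the stated 100. Truncating to 30 diseased gives 30 / 0.30 = 100 exactly.
- Adding 5 for dropout gives the stated 105.

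The point below does not depend on this small difference. The plan states no precision target for complications.

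**2. Timeline from the text, with the procedure on day 0.**

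| Time | What the plan states |
|---|---|
| Day −1 to day +1 | Antibiotic course |
| Day 0 to the next morning | Complication monitoring |
| Next morning to LDT, at most 7 days | No complication recording described |
| LDT | Tubal patency recorded; no complication check described |

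**3. What a zero count would bound.** With 0 events in n women, the one-sided 95% upper limit is 1 − 0.05^(1/n). For n = 105 this is 1 − 0.05^(1/105) = 0.028, or 2.8%. If only 100 women are evaluable, it is 3.0%.

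This limit applies to events that the window can see. Let f be the fraction of infections that become apparent overnight. The data then bound p × f, where p is the true infection rate, so the bound on p is 2.8%/f:

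- f = 1: 2.8%
- f = 0.5: 2.8% / 0.5 = 5.6%
- f = 0.25: 2.8% / 0.25 = 11%

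**4. Chance of recording at least one infection.** This is 1 − (1 − p × f)^105. Both p and f are assumed.

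| Assumed true rate p | f = 1 | f = 0.5 | f = 0.25 |
|---|---|---|---|
| 1% | 0.65 | 0.41 | 0.23 |
| 2% | 0.88 | 0.65 | 0.41 |
| 3% | 0.96 | 0.80 | 0.55 |

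For example, at p = 2% and f = 0.5: 1 − 0.99^105 = 0.65.

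**The case against.** The strongest objection is that the documents give no onset time and no infection rate, so nothing in them shows that an infection would appear after the first night. That stands. It is why f is an assumption shown over a range, with f = 1 (nothing missed) included.

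A reader might infer that the complication rate cannot capture infection at all, or would be close to zero by construction. The documents do not support this. Step 13 covers any procedure-related complication, so an infection apparent overnight would be recorded. Outcome 5 has an open list and no time limit, and a later infection could come to light at LDT even though no recording is planned there.

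A reader might also take 2.8% as the size of the defect. It is not: that figure follows from n = 105 alone and would be the same under any window. Only the division by f relates to the window, and f is unknown.

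It is also fair to say that the plan promises no separate infection rate, makes no safety claim and sets no safety hypothesis. Its objective is diagnostic accuracy. This limits the importance of the point without removing it, because an overall complication rate is promised and infection is a risk that the plan itself raises.

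Finally, the gain from a later check may be modest. Section 8 places HyLiFoSy-PD a few days before LDT in one place and within a week in another, so the added window could be short. Infection first seen after LDT remains hard to attribute whatever is done. Both limits stand.

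**Conclusion.** The point holds in a limited form. Overnight is the only complication follow-up that the plan states, and no recording is described from then until LDT. The rate reported for secondary outcome 5 may therefore miss an infection that becomes apparent in that interval.

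The size cannot be fixed from the documents. Under assumed capture fractions from 1 down to 0.25, a zero count in 105 women would be compatible with an infection rate of up to about 2.8% to 11%. The conclusion needs only that some infections could become apparent after the first night. It does not claim that most would.

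Only a secondary safety outcome is touched. A reader might suspect bias in the sensitivity and specificity estimates, but nothing in the documents establishes that, and the sample size does not depend on the window. This is a cheap improvement and not a flaw that threatens the trial.

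**What to change.** - In section 9, define the collection window for secondary outcome 5 as running from the HyLiFoSy-PD procedure to LDT admission, and name infection as a component with a stated definition.
- In section 8, add to step 14 a short fixed checklist of signs and symptoms of pelvic infection, completed at LDT admission before laparoscopy starts. It should not disclose the HyLiFoSy-PD patency result, so that the endoscopist stays blinded.
- In section 11, report overnight events and events first recorded at the pre-LDT check separately, each with its denominator.
- State in the report that the rate covers events up to LDT only, because later events cannot be clearly attributed to HyLiFoSy-PD.

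The cost is one short form per woman at a visit that already takes place, with no extra visit or procedure. The change concerns data collection only and proposes nothing about clinical management.
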